**Immediate Fit Using Innovative Technology Transtibial & Transfemoral
Prostheses**

iFIT Prosthetics, LLC

May 13, 2022

NCT02886936

Transtibial Device Testing Protocol

Location: Penn Medicine Department of PM&R Gait Lab

PI: [name], MS, MD

Research Coordinator: [name], MS

Funding: National Institutes of Health, National Institute on Aging (grant nos. 2SB1AG050430-06 and 2R42AG050430-04) and the National Institute of Child Health and Human Development and National Center for Medical Rehabilitation Research (grant nos. 2R42 HD069067-02 and 1R41HD069067-01).

Overview: Persons with limb loss were recruited for a two week home trial to test out an immediate fit, adjustable, lower limb prosthesis.

Key inclusion criteria:

i) transtibial level of amputation, ii) ambulate with or without a gait assistive device or has the potential to ambulate with gait assistive device if this is their first prosthesis, iii) has been cleared by surgeon to be fit with prosthesis or is already wearing prosthetic device. We will include persons with limb loss due to cancer (very rare), trauma, and dysvascular causes (diabetes).

Key exclusion criteria:

Subjects will be excluded if; i) they have skin ulcerations on the residual limb, ii) have other central nervous system disorders such as strokes and brain injuries that interfere with safe ambulation and gait testing, or iii) severe phantom or limb pain.

Procedures:

Full informed consent for all subjects will be obtained. If an adolescent participates, consent will be obtained from both the parent and the child. Participation will take approximately 3.0 hours and will be conducted in one of our outpatient therapy areas. Subjects, after signing an informed consent, will be fit with the prototype device that uses a buckle system and easily adjusts to conform to the residual limb and provide optimal alignment. The principal investigator ([name]) who lead the Phase I study and who has considerable clinical experience in optimally aligning the device, will fit and test all subjects. The optimal height will be achieved by using the proper size of shank connector (multiple length connectors for the foot are precut) and all subjects will use a SACH foot with their current shoes. Subjects will then ambulate on a flat open surface with the principal investigator providing contact guard with a safety waistbelt.

They will walk for three minutes. If they are comfortable and stable, they will walk an additional 5 minutes at their self-selected walking speed with standby assistance from the principle investigator. Following this ambulation testing, they will then remove the device and liner and re-don the device by themselves. They will then walk for an extended period up to an hour. We will perform gait analysis on selected amputees by placing small reflective markers on their lower body and asking them to walk several times in the Gait and Biomechanics Lab. They will then complete our outcome survey to grade, comfort, fit, ease of use, pain and functionality on an interval scale of 1 to 10. Subjects will grade these domains for the prototype as well as their conventional prosthesis. This testing is safe and of minimal risk. In our early testing with 18 subjects there were no balance losses, skin irritations, or adverse events.

2 Week Home Trial: These participants will be fit with the device by the Principal Investigator and it will be optimally aligned in the laboratory at the Pennsylvania Institute for Rehabilitation (PIRM). They will walk around the building for about 30 minutes in order to insure the fit and alignment are optimal. During this time they will put on and take off the device four times, walk up and down the therapy stairs at the physical therapy department, and perform several sit to stand movements. The participant will need to demonstrate that they can fully utilize the device without the investigators assistance prior to taking it home.

The amputee will be instructed to wear the device as they normally would. They will be asked to refrain from wearing the device during inclement weather (ice or snow), running or highly strenuous activities. Each patient has their own custom prosthesis and should any problems develop, they are to go back to using their conventional device and call the study coordinator. For new amputees without a conventional prosthesis, we will give them some gait training during their first visit. They will then be instructed to bring the prosthesis to physical therapy to continue training with it.

They will be given the phone number of both the Principal Investigator, [name], and the Research Coordinator, [name], to report any issues with the device. The participant will be contacted after the first 24 hours, and again after the first week by the Research Coordinator to assess their progress and record any issues.

They will be given a pre and post prosthetic outcome survey for them to rate the comfort and functionality of the device. If the amputee finds the device comfortable and would like to test it beyond the two week period, they will be given the option to do so. This is provided they are willing to come in for regular period appointments to assess their limb and the mechanical aspects of the device. The participants will still need to alert either the Research Coordinator or the Principal Investigator if any issues arise such as mechanical problems with the device or skin breakdown. They will be contacted by the research coordinator at Penn 3-5 days after fitting, and also be scheduled for a two week check-up. Amputees may schedule an appointment to have their device adjusted any time during this period if they feel it is needed.

Transfemoral Study Additional Procedures: Measurements will be taken of the participant's limb at the proximal, mid and distal point. Measures will be taken both on skin and while wearing a liner. Once the prosthesis is fit and the optimal tightness is achieved, the PI will mark where the flaps overlap. The participant will remove the socket, and the socket will be re-buckled to the circumference they had while wearing it. Measures will be taken using an Internal Socket Measurement Gauge of the proximal, mid and distal points of the inside of the socket. This will be repeated for the conventional device and recorded.

For persons with recent limb loss or needing PT: As the iFIT system is commonly fit as a preparatory device to accommodate volume changes during the first year, we are including this population. These persons will be fit in the gait lab as described above. They will sign a form that describes how they will obtain outpatient physical therapy following the fitting. They will only wear the prosthesis during the therapy. Once the therapist clears them for independent use, they may continue to wear on their own at home. They will still have a follow up conducted at Penn to assess the device.

2 Week Follow Up: The participant will return two weeks following the initial fitting. They will fill out the PEQ – based outcome questionnaire again on the iFIT socket. They will complete a gait analysis wearing the iFIT Prosthesis as well as their conventional prosthesis. They will also have socket internal pressure measurements taken using Fuji-film prescale. This will be placed in five locations on top of the silicone liner: anterior proximal, anterior distal, lateral, medial and posterior. They will ambulate in the lab for two minutes and then have the papers removed for analysis. This will be completed on both sockets. The PI will also inspect the participant's skin for limb ischemia, edema, redness or skin breakdown. The socket will also be inspected for any wear or mechanical breakdown.

Data Storage:

All data on paper is kept in a locked filing cabinet which is accessed only by the Research Coordinator. Computer files are kept on PC's managed by Penn Medicine Academic Computing Services (PMACS). Key study personnel other than the Research Coordinator ensured data collected through questionnaires and Fujifilm was valid and correct. All data for analysis is de-identified prior to sending to the statistician for analysis.

Transtibial Statistical Analysis Plan:

Standard summary statistics, such as mean and SD or frequency and percentage were used to describe the study population. To test for differences in questionnaire score and pressure data between prosthetic devices, paired t-tests were used. For the questionnaire score analyses, two separate paired t-tests were performed.

One for participants with a complete set of questionnaire scores; another used an intention to treat analysis that included the 4 noncompleters with no questionnaire scores at 2 weeks for the iFIT device. For this latter analysis, it was assumed that the

non-completers would have worse scores on the iFIT device than reported with their conventional device at the first visit. Therefore, to impute a value for the iFIT device, the mean difference between devices (own vs iFIT) for the participants who completed testing ($n = 22$) were subtracted from the scoring for the noncompleters regarding their conventional devices at the first visit. This modeled a worse-case scenario (less satisfaction) with the iFIT device compared

to the conventional device for people who dropped out. To test for differences between prosthetic devices for the gait biomechanical measures, a single-group 2-way analysis of variance with repeated measures, where leg (involved, unininvolved) and device (own, iFIT) were the repeated measures. All analyses were performed using SAS statistical software (version 9.4, SAS Institute, Cary, NC).

Transfemoral Statistical Analysis Plan:

A sample size of 12 to 14 was predicted to achieve $>80\%$ power, with an alpha of 0.05, using a clinically meaningful difference of 1 (effect size) on an individual PCUQ question (range of score, 1-5) with SD of the mean difference as large as 1.3. To describe the study population, frequencies and percentages were calculated for categorical variables, and means and standard deviations were calculated for continuous variables. To compare responses to the individual PCUQ questions and the patient satisfaction score between the iFIT device and patients' conventional device, paired t-tests were used because the mean differences were approximately normally distributed, with only mild left skew and lightly tailed. Results are presented as mean difference 95% confidence intervals between the adjustable socket and the conventional device. All analyses were performed using SAS statistical software (version 9.4, SAS Institute, Cary, NC). Data were collected by the study coordinator and maintained by her independent of the principal investigator. All statistical analyzes were performed by the biostatistician ([name]) independent of the principal investigator.

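### The transfemoral SAP powers and compares 1–5 PCUQ items that no procedure names, and on that scale a two-sided paired t-test has about 68–76% power, not over 80%

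*Combined protocol and SAP*

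**What the plan says.** Questionnaires appear in four places.

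- **Procedures** (under the title Transtibial Device Testing Protocol): after the walking tests, participants rate several domains, including "pain and functionality on an interval scale of 1 to 10", for both the prototype and their conventional prosthesis.
- **2 Week Home Trial**: "They will be given a pre and post prosthetic outcome survey for them to rate the comfort and functionality of the device". The survey is not named and has no scale.
- **2 Week Follow Up**: participants complete the PEQ-based "outcome questionnaire again on the iFIT socket". No scale is given, and no earlier section uses the PEQ name.
- **Transfemoral Statistical Analysis Plan**: 12 to 14 participants are said to give more than 80% power at alpha 0.05, "using a clinically meaningful difference of 1 (effect size) on an individual PCUQ question (range of score, 1-5", with an SD as large as 1.3. The analysis is introduced by "To compare responses to the individual PCUQ questions and the patient satisfaction score", with paired t-tests and 95% confidence intervals.

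The only section written specifically for the transfemoral cohort opens "Transfemoral Study Additional Procedures: Measurements will be taken of the participant's limb at the proximal, mid and distal point". It goes on to internal socket measurements and mentions no questionnaire.

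**The concern.** PCUQ occurs only in the transfemoral SAP. It is not spelled out, has no administration schedule, and is not linked to the 1–10 survey, the pre/post survey or the PEQ-based questionnaire. The patient satisfaction score is not named in any procedure either. Yet these two measures carry the powered endpoint and the main comparison of this cohort.

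Two things are at stake.

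- A paired t-test needs both devices scored on the same form. For the transfemoral cohort the plan does not say so, and at 2 weeks it describes the questionnaire for the iFIT socket only.
- The power statement is in the units of a 1–5 item. It cannot be checked against the data collection until the plan says which form is scored 1–5. Even on that scale, the stated power does not follow from a two-sided test.

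**Working it through.** **1. Procedures and SAP side by side**

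| Section | Instrument | Scale | Devices rated |
|---|---|---|---|
| Procedures | outcome survey | 1–10 | both |
| 2 Week Home Trial | pre/post survey, unnamed | none stated | the study device |
| Transfemoral Study Additional Procedures | none | – | – |
| 2 Week Follow Up | PEQ-based questionnaire | none stated | iFIT |
| Transfemoral SAP | PCUQ items | 1–5 | both compared |
| Transfemoral SAP | patient satisfaction score | none stated | both compared |

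No name in the SAP rows matches a name in the rows above. The only scale in the procedures (1–10) differs from the only scale in the transfemoral SAP (1–5).

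**2. Reproducing the stated power**

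Inputs, all from the Transfemoral SAP: difference 1, SD 1.3, alpha 0.05 (sidedness not stated), n = 12 to 14, paired t-test. The 1.3 is read as the SD of the within-person differences.

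Power comes from the noncentral t distribution with n − 1 degrees of freedom and noncentrality (1/1.3) × √n. That is 0.769 × 3.464 = 2.66 at n=12 and 0.769 × 3.742 = 2.88 at n=14.

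| n | One-sided 5%, paired t | Two-sided 5%, normal approximation | Two-sided 5%, paired t |
|---|---|---|---|
| 12 | 80.3% | 76.0% | 68.0% |
| 13 | 83.3% | 79.2% | 72.1% |
| 14 | 86.0% | 82.1% | 75.8% |
| 16 | 90.1% | 86.8% | 82.0% |

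The claim of more than 80% reproduces across 12 to 14 only in the one-sided column. The two-sided normal approximation gives n = (1.3 × (1.960 + 0.842))² = 13.26, rounded up to 14, so it supports only the top of the range. The two-sided paired t-test, which is the test that corresponds to a 95% confidence interval, first exceeds 80% at n=16 (n=15 gives 79.1%).

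Put the other way, the largest SD that still gives 80% two-sided power is 1.125 at n=12, 1.181 at n=13 and 1.234 at n=14, all below 1.3.

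**3. Does a change of scale alter this?**

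A 1–5 item spans 4 points and a 1–10 item spans 9, a ratio of 9/4 = 2.25. If both inputs are stretched, the difference becomes 2.25 and the SD 1.3 × 2.25 = 2.925. The ratio 2.25/2.925 = 0.769 equals 1/1.3, so power stays at 68.0% and 75.8%. Power changes only if the difference and the SD are not restated together.

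**The case against.** The strongest reply is that this is a labelling gap, and much of that stands.

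- The word "again" in the 2-week text, and a survey described as both pre and post, point to one instrument given twice. The 1–10 sentence also has both devices graded on one survey.
- The 1–10 survey sits under a transtibial title, in the description of the single test session. That the transfemoral cohort inherits it is an inference from the word Additional in its own section. The pre/post survey or the PEQ-based questionnaire could be the 1–5 form.
- The transfemoral SAP is written after the event. It describes the distribution of the paired differences and says that the data were collected.

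A reader might therefore infer too much in three ways. One is that the conventional and iFIT scores came from different instruments, so that the paired difference is uninterpretable; no text says this. Another is that the powered outcome was never collected; the SAP's account of observed differences points the other way. The third is that power falls to about 19–22%. That figure comes from stretching the SD to 2.925 while holding the difference at 1 point, and the documents propose no 1-point difference on a 1–10 scale. It also depends on the SD assumed: at 2.0 the result would be 35–41%.

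What the reply does not remove is that no section states the link between the PCUQ and any administered form. If the transfemoral cohort inherits the earlier surveys, the stated scales conflict or are absent. If it does not, no questionnaire is specified for it at all. Nor does the reply touch the power on the 1–5 scale.

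**Conclusion.** The point holds as an inconsistency between procedures and SAP on the powered transfemoral endpoint, together with a power figure that needs restating. It is not evidence of invalid pairing or missing data.

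On the SAP's own 1–5 scale, power is about 68% (n=12) to 76% (n=14) rather than above 80%. This rests on a two-sided 5% test, which the SAP does not state but which its 95% confidence intervals imply, and on 1.3 being the SD of paired differences. If a one-sided test was intended, the stated figure is right and only the sidedness is missing. The shortfall comes from sidedness and the t distribution, not from the naming of the instrument, so the two parts should be answered separately.

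**What to change.** 1. In the procedures, state which questionnaire is the PCUQ and how it relates to the 1–10 survey, the pre/post survey and the PEQ-based questionnaire. Spell out the name and give the items, scoring range and direction. Do the same for the patient satisfaction score.
2. State that, in the transfemoral cohort, the same form is scored for the conventional device at the first visit and for iFIT at 2 weeks. If the timing or form differed, say what was done.
3. Use one name for each instrument in the procedures and the SAP.
4. Restate the power in that instrument's units, with the sidedness. On the 1–5 scale with a two-sided test, report about 68% to 76% for 12 to 14 participants. If the design was one-sided, say so and reconcile that with the 95% confidence intervals. If the form is not scored 1–5, give both the meaningful difference and the SD on its own scale.

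The cost is a few sentences and one restated power figure. No new data are needed if the same form was used for both devices.

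### Outpatient therapy after fitting can fall between the conventional rating and the 2-week iFIT rating, and the transtibial questionnaire comparison does not separate it from the device

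*Combined protocol and SAP*

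**What the plan says.** The section on recent limb loss and therapy widens the study population: "For persons with recent limb loss or needing PT: As the iFIT system is commonly fit as a preparatory device". Of these participants it says "They will sign a form that describes how they will obtain outpatient physical therapy following the fitting" and, until a therapist clears them for independent use, "They will only wear the prosthesis during the therapy". The key inclusion criteria also admit people who already wear a prosthesis.

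For ratings at the first visit, the Procedures section says "Subjects will grade these domains for the prototype as well as their conventional prosthesis". Under 2 Week Follow Up, the questionnaire is repeated on the iFIT socket, and no repeat for the conventional device is described. Gait differs: "They will complete a gait analysis wearing the iFIT Prosthesis as well as their conventional prosthesis". Pressure film is likewise used in both sockets at that visit.

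The Transtibial Statistical Analysis Plan states: "To test for differences in questionnaire score and pressure data between prosthetic devices, paired t-tests were used". It gives 22 completers and 4 noncompleters, and imputes the latter from the completers' mean difference and the first-visit conventional scores. Neither analysis plan has a therapy variable, exclusion, subgroup or sensitivity analysis.

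**The concern.** For a therapy recipient who owns a conventional prosthesis, the conventional score predates therapy and the 2-week iFIT score can follow it. The graded domains include comfort, ease of use, pain and functionality, which gait training could plausibly improve. Any such gain sits on the iFIT side of the pair. The paired t-test would then estimate device plus therapy for these people and device alone for the rest, under a single label. Because the number of therapy recipients among the pairs is not reported, a reader cannot judge how far this matters.

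**Working it through.** **Inputs from the documents.** 22 completers and 4 noncompleters (Transtibial Statistical Analysis Plan); questionnaire scale 1 to 10 (Procedures). The plan has no figure of its own on therapy to reproduce. Its only sample-size figure, 12 to 14 for the transfemoral study, plays no part here.

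**Assumed, because the documents do not give them.** The number k of pairs with therapy, the gain g in points, an SD of paired differences of 2 points (range 1.5 to 2.5), no true device effect, and higher scores being better. The therapy group's follow-up is taken to be the 2-week visit.

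**Step 1: who can be affected.** Someone with no conventional device supplies no pair. Bias needs a participant who both receives therapy and owns a conventional prosthesis. The wording of the therapy section, together with the inclusion criteria, allows this.

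**Step 2: timing.** The conventional rating is at the first visit and the repeat iFIT rating at 2 weeks. The plan names the first-visit conventional score explicitly only for the imputation. For completers its use follows from the absence of any 2-week conventional questionnaire.

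**Step 3: size.** Mean bias = k × g / n with n = 22. Rejection rates are simulated for a two-sided 5% paired t-test at SD 2.

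| k | g (points) | Bias toward iFIT | Rejection with no device effect |
|---|---|---|---|
| 2 | 0.5 | 2 × 0.5 / 22 = 0.05 | about 5% |
| 3 | 1 | 3 × 1 / 22 = 0.14 | 5.7% |
| 5 | 2 | 5 × 2 / 22 = 0.45 | 13.4% |
| 7 | 2 | 7 × 2 / 22 = 0.64 | 22.9% |

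In the last two rows nearly all rejections favour iFIT. For SD 1.5 to 2.5, the last row ranges from 34% down to 17%.

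**Step 4: imputation.** Let b be the bias in the completers' mean difference (iFIT minus own). If that difference is subtracted from the 4 noncompleters' conventional scores, as the stated worst-case aim implies, each contributes −b. The 26-person mean then carries (22b − 4b)/26 = 0.69b; for b = 0.45 that is 0.31. If instead own minus iFIT is subtracted, each contributes +b and the full b remains. Under neither reading does the intention-to-treat analysis remove it.

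**Step 5: gait and pressure.** Both devices are tested at the same visit, after the same therapy. A gain common to both devices cancels in the difference. Only a practice effect specific to iFIT could remain.

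**The case against.** The affected group may be small or empty. The therapy section justifies itself by first-year volume change, and the home-trial text on therapy concerns people with no comparator: "For new amputees without a conventional prosthesis, we will give them some gait training during their first visit", followed by "They will then be instructed to bring the prosthesis to physical therapy to continue training with it". They cannot bias a paired test. This stands as a limit on scope, but it does not exclude a prosthesis owner who needs therapy.

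The larger problem may be timing. The repeat rating is on iFIT only for every participant, so removing therapy recipients leaves that asymmetry in place. This also stands. The sensitivity analysis isolates therapy and does not cure the timing.

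The inputs to the size are all assumed, and 22.9% needs about a third of the pairs to be in therapy with a 2-point gain each. That is correct, and it is why the request is for a count and a sensitivity analysis. It is no reason to replace the main analysis.

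A reader might infer three stronger things that the documents do not support:

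- **Therapy was given in iFIT only.** The text restricts where iFIT is worn before clearance. It does not bar the conventional device from therapy.
- **Gait and pressure are biased in the same way.** Same-visit testing of both devices removes any shared gain.
- **The transfemoral comparison is equally affected.** The timing of its PCUQ ratings is not stated, so therapy cannot be placed between them.

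**Conclusion.** The point holds for the transtibial questionnaire. For therapy recipients who own a conventional prosthesis, therapy can fall between the two ratings, and the pooled paired t-test cannot separate its effect from the device. The bias also enters the noncompleter imputation. Under the assumptions above it runs from about 0.05 to 0.64 points toward iFIT, with rejection of a true null in about 5% to 23% of trials at SD 2. The documents do not show that therapy gains were in fact counted as a device effect, only that the plan would not detect it. For gait and pressure, only an iFIT-specific practice effect is possible, and its size is unknown. The point is worth acting on because the check is cheap.

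**What to change.** Add one yes/no variable for physical therapy between fitting and the 2-week visit. The form these participants sign is a starting point for identifying them. Report how many of them contributed pairs. Keep the pooled paired t-test as planned. Specify, before it is run, a sensitivity analysis of the questionnaire difference that excludes them, and report therapy recipients separately as iFIT plus therapy. Attribute to the device only a difference that holds without them, judged on the estimate and its interval as well as the p-value. The analysis plan is written in the past tense, so if results are already known, label the analysis as added afterwards.

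Where first-visit ratings of both devices exist, showing that same-day comparison as well costs no new data and precedes therapy. For the transfemoral study, state when the PCUQ ratings were taken; the same sensitivity analysis is needed only if therapy could fall between them.

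The cost is precision in the smaller set. If 5 of 22 pairs are excluded, the standardised difference detectable with 80% power (two-sided 5%, noncentral t) rises from 0.63 to 0.72. A result that loses significance there may reflect the smaller number of pairs alone.

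### Device order in the 2-week gait and pressure runs is neither specified, randomised nor modelled, so an order effect can pass as a device effect

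*Combined protocol and SAP*

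**What the plan says.** **Procedure (2 Week Follow Up).** For gait: "They will complete a gait analysis wearing the iFIT Prosthesis as well as their conventional prosthesis". For socket pressure, film is placed at five sites on the liner. Then "They will ambulate in the lab for two minutes and then have the papers removed for analysis", and "This will be completed on both sockets". The section gives no rule for which device goes first, for rest between runs, or for recording the sequence. No other section supplies one.

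**Analysis (Transtibial Statistical Analysis Plan).** For pressure: "To test for differences in questionnaire score and pressure data between prosthetic devices, paired t-tests were used". Gait uses "a single-group 2-way analysis of variance with repeated measures", "where leg (involved, unininvolved) and device (own, iFIT) were the repeated measures". Leg and device are the only factors. There is no order, period or sequence term, and a single-group model has no sequence groups.

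**Transfemoral Statistical Analysis Plan.** It names paired t-tests for PCUQ items and patient satisfaction only. It states no gait or pressure test.

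**The concern.** Testing each participant in both devices removes differences between people. It does not remove a difference between the first and second run of a session. Between the runs the participant takes off one socket, puts on another and walks again, so fatigue, practice or a change in limb volume could shift the second measurement whichever device is worn. The protocol itself describes iFIT as accommodating volume change. That passage concerns the first year after limb loss, so change within a session is a plausible mechanism and not a documented one.

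Gait and pressure are the instrumented comparisons, the ones least dependent on participant opinion. If the order is left to habit, a shift between runs goes into the iFIT-minus-own difference. It could create a difference that the devices do not cause, or hide one that they do.

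**Working it through.** **Inputs.**
- Order rule: none stated (2 Week Follow Up).
- Analyses: paired t-test for pressure; leg-by-device ANOVA for gait (Transtibial SAP).
- n: not stated for gait or pressure. I assume 22, which the Transtibial SAP gives as the number of completers in its questionnaire imputation.
- Order effect: no size is given in the documents. I assume values from 0.2 to 0.75 SD of the paired difference.
- Test: I assume a two-sided 5% level.

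The plan has no figure of its own to reproduce here. Its only sample-size statement (12 to 14) is for a transfemoral PCUQ question and does not bear on these runs.

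**Step 1: bias.** Let δ be the true device effect (iFIT minus own) and o the order effect (second run minus first). A participant who wears iFIT second has expected difference δ + o; one who wears it first has δ − o. With share p wearing iFIT second, the mean paired difference has expectation

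δ + p·o − (1 − p)·o = δ + (2p − 1)·o.

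- One order for all (iFIT second): p = 1, bias = o. If iFIT is first for all, bias = −o.
- 16 of 22 one way, 6 the other: 2 × 16/22 − 1 = 10/22, so 45% of o.
- 11 and 11: p = 0.5, bias = 0.

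In the gait ANOVA, an order effect common to both legs enters the device main effect in the same way. Only a leg-specific order effect would reach the leg-by-device term.

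**Step 2: false-positive rate with one common order, δ = 0.** The paired t statistic is noncentral t with 21 df and noncentrality o × √22 = 4.690 × o. The critical value is 2.080.

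| Assumed o (SD of paired difference) | Noncentrality | Rejection rate |
|---|---|---|
| 0.2 | 0.94 | 14.6% |
| 0.3 | 1.41 | 26.9% |
| 0.5 | 2.35 | 60.9% |

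**Step 3: the same test when orders are mixed.** The common-order row uses the Step 2 formula; the mixed rows are simulated (100,000 runs each).

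| Split of orders | o = 0.25 | o = 0.50 | o = 0.75 |
|---|---|---|---|
| 22:0 | 20% | 61% | 92% |
| 16:6 | 7% | 13% | 20% |
| 11:11 | 4.4% | 2.9% | 1.4% |

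With balanced orders the test falls below 5%, because the unmodelled order effect inflates the residual variance.

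**Step 4: what a period term can do.** With k participants in one order and n − k in the other, the period-adjusted device estimate has variance ¼(1/k + 1/(n − k)) in units of the variance of a paired difference.
- 11:11 gives ¼(1/11 + 1/11) = 0.0455, equal to 1/22. Adjustment costs no precision beyond 1 degree of freedom.
- 16:6 gives ¼(1/16 + 1/6) = 0.0573. Adjustment is possible but less precise.
- 22:0 cannot be evaluated. Device and period are the same variable, and no model term separates them.

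**The case against.** The best counter-argument is that the documents are silent on order, and silence is not evidence of a fixed order. That is right. A reader might infer from the gait sentence, which names iFIT first, that iFIT was always tested first, and so that any order effect is counted in full as a device effect. The sentence lists two devices and sets no sequence, and the pressure text says only that both sockets are done. Full confounding is the limiting case, and the Step 2 rates belong to that case alone. If the orders happened to balance, the bias is zero and the test is conservative. Mixing that was not randomised could, however, bring selection of its own.

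Three further limits stand:
- The value n = 22 is borrowed from the questionnaire analysis. A transfemoral n should not be used at all, since that SAP states no gait or pressure test.
- The order effect may be small. Each pressure run lasts two minutes, and the documents give no size for fatigue, practice or volume change.
- The SAP is written in the past tense, so randomisation cannot repair data already collected.

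None of this removes the gap. No section sets the order, neither analysis accounts for it, and a reader cannot rule out the fully confounded case.

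**Conclusion.** The point holds in conditional form. Device order in the 2-week gait and pressure runs is unspecified, not randomised and not modelled. The device difference carries a bias of (2p − 1) times any order effect. If one order was used throughout, device and order cannot be separated by any analysis.

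The rejection rates of about 15%, 27% and 61% rest on four assumptions: one common order, no device effect, n = 22, and order effects of 0.2, 0.3 and 0.5 SD. They show sensitivity and do not estimate what happened in this trial. The documents support neither a claim that the order was fixed nor a claim that the reported tests did reject too often.

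The scope is limited to gait and pressure. The questionnaire scores do not come from these runs, so their comparisons are untouched. This should be corrected: the size of the bias is unknown, but it is avoidable at almost no cost.

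**What to change.** **For runs still to be done, or a further study with this design.** Randomise participants who have a conventional prosthesis 1:1, in small permuted blocks, to iFIT-first or own-device-first for the 2-week gait and pressure runs. First-time users without a conventional device have no second device to test and are outside the scheme. Record the order actually used. Add a period term to the gait ANOVA, and analyse the paired pressure differences adjusted for sequence. This adjustment assumes that any carry-over from the first run to the second is the same for both devices, so the procedure should also state the interval between runs. The cost is a short randomisation list, a line or two in the visit procedure, one model term and 1 degree of freedom, with no extra visits or participants.

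**For data already collected.** Report the order used and the number of participants in each order, with the n for gait and for pressure. If the order varied and was recorded, give an order-adjusted analysis beside the stated one, noting that an unrandomised order may itself be selective. If the order was the same for all or was not recorded, state that device and order effects cannot be separated for these outcomes. The cost is a check of the visit records and, where possible, one additional analysis.
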